9.1. Ethics & Regulatory Approvals

The study will comply with the principles of the Declaration of Helsinki and the principles of Good Clinical Practice (GCP) and in accordance with all applicable regulatory requirements including but not limited to the Research Governance Framework. This protocol and related documents

will be submitted for review and receive approval from the Research Ethics Committee (REC). Additionally, local R and D approval will be sought in all participating centres. Any future amendments, progress and final reports will be submitted as required. The study and any amendments will only be implemented following Ethics Committee and Trust approval by the R&D Department in each participating centre.

9.2. Assessment of Efficacy for MRI and transvaginal ultrasound

Image quality will be assessed by the research team.

9.3. Procedures for Assessing Efficacy Parameters

The within the research programme. Image quality is reviewed weekly and persisting issues analysed and appropriate action taken. This occasionally involves calling scanner engineers to fix a fault.

9.4. Specification, Timing and Recording of Safety Parameters

CRAFT-IMG: Each woman is assessed prior to MRI examination to ensure there are no contraindications to scanning. This includes a health check and a detailed metal safety check. Women are carefully placed inside the scanner to ensure comfort and safety. We are also in constant contact with the woman during the examination so if she is uncomfortable or feels unwell we can remedy the situation immediately. Full resuscitation equipment is always available outside the scanner and staff are trained in basic life support. Any adverse events are recorded as for any Trust patient.

9.5. Safety

9.5.1 Assessment of Safety

The Data Monitoring Committee (DMC) will be convened to ensure the wellbeing of study participants and the quality of the data collected (see below section 9.8). The committee will periodically review study progress and outcomes as well as reports of serious adverse events (SAEs). The DMC will, if appropriate, make recommendations regarding the continuance of the study or modification of the study protocol.

9.5.2 Procedures for Recording and Reporting Adverse Events

Serious adverse Event (SAE), Serious Adverse Reaction (SAR)

The Medicines for Human Use (Clinical Trials) Regulations 2004 and Amended Regulations 2006 gives the following definitions:

Adverse Event (AE): Any untoward medical occurrence in a subject to whom a medicinal product has been administered including occurrences which are not necessarily caused by or related to that product.

Adverse Reaction (AR): Any untoward and unintended response in a subject to an investigational medicinal product which is related to any dose administered to that subject.

Unexpected Adverse Reaction (UAR): An adverse reaction the nature and severity of which is not consistent with the information about the medicinal product in question set out in the Investigator's Brochure (IB) relating to the trial in question (for any other investigational product)

Serious adverse Event (SAE) or Serious Adverse Reaction (SAR) is:

Any adverse event, adverse reaction or unexpected adverse reaction, respectively, that

- Results in death
- Is life-threatening
- Required hospitalisation or prolongation of existing hospitalisation, excluding admission for birth or unrelated pregnancy condition
- Results in persistent or significant disability or incapacity
- Is otherwise considered medically significant by the principal investigator.

All AEs and SAEs must be recorded from the time a participant is randomized to treatment until 30 days after stopping taking study drug and until pregnancy outcome (28 days after delivery). The Investigator should ask about the occurrence of AEs/SAEs at every visit during the study. Open-ended and non-leading verbal questioning of the participant should be used to enquire about AE/SAE occurrence. Participants should also be asked if they have been admitted to hospital, had any accidents, used any new medicines or changed concomitant medication regimens. If there is any doubt as to whether a clinical observation is an AE/SAE, the event should be recorded. Hospitalisations for treatment planned prior to randomisation and hospitalisation for elective treatment of a pre-existing condition will not be considered as an SAE. Complications occurring during such hospitalisation will be AE/SAEs.

Important Medical Events (IME): Events that may not be immediately life-threatening or result in death or hospitalisation but may jeopardise the patient or may require intervention to prevent one of the other outcomes listed in the definition above should also be considered serious.

9.5.3 Adverse events which do not require reporting

Expected serious adverse events (SAEs) are those events which are expected in the patient population or as a result of the routine care/treatment of a patient. The interventions they will be receiving are those which would be offered routinely in clinical practice. Cervical cerclage insertion is an established surgical procedure, which is associated with minimal risks. These

include infection, miscarriage, bleeding, difficulty with suture removal and preterm prelabour rupture of membranes.

Serious adverse events and serious adverse reactions (SARs) which are unrelated to these clinical procedures will be reported as SAEs.

Events that are primary or secondary outcome measures are not considered to be SAEs and will be reported in the normal way, on the appropriate electronic case report form.

Maternal:

- Premature labour
- Premature rupture of membranes
- Chorioamnionitis

Infant:

- Perinatal death (unless unexpected at this gestation)
- Low birth weight
- Requirement for supplemental oxygen or ventilation support
- Complications of prematurity (e.g. IVH, NEC, encephalopathy, seizures, hypoglycaemia) unless unexpected in this population
- Admission of the baby to the neonatal unit

In addition the following common pregnancy complication events will not be considered SAEs: hospitalisation for pre-eclampsia or pregnancy induced hypertension, hospitalisation for symptoms of preterm labour (e.g. rupture of membranes, vaginal bleeding); hospitalisation for maternal discomfort; hospitalisation for rest; hospitalisation for observation or monitoring for which the woman is admitted for a period of less than 12 h; delivery complications such as caesarean section or postpartum haemorrhage.

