There are multiple factors which predispose women to preterm birth such as surgery to the neck of the womb, previous preterm birth and multiple pregnancies. A new factor now found to be contributing to this risk is if the mother has had a previous full dilatation caesarean section (FDCS) in labour particularly when she is 10cm dilated. We don't know how significant this risk is in the UK and the mechanism is not proven but what is known is that it particularly affects pregnancies under 28 weeks and also results in many late miscarriages (14-23⁺⁶ weeks). It is thought it occurs because a cut is made to the cervix (neck of the womb) at the time of the caesarean which weakens it. We do not routinely look for a scar on transvaginal ultrasound when measuring the cervical length (CL).

New NHS Commissioning guidelines(1) and *Saving Babies Lives Care Bundle*(2) has now recommended to screen all women with a previous FDCS because of this new widely reported risk. We don't know whether a cerclage (stitch) inserted into the cervix, first line prophylactic treatment in many UK units for a short cervix (≤ 25 mm), works in this group of women. We have never imaged the cervix looking for injury in this FDCS group of women and compared it to our assessment with routine transvaginal ultrasound. We also do not know if a cut off of ≤ 25 mm is a short cervix in women with a previous FDCS. Furthermore, we do not know how many women with a previous caesarean at 4-9cm dilatation has a risk of preterm birth in the future nor if our current tests of cervical length and fibronectin test work well to predict preterm birth in these women. A cerclage for a short cervix ≤ 25 mm in women with a previous FDCS is not part of routine care. Hence why there is a three-pronged approach in CRAFT:

1. Observational study of women with a previous caesarean in labour
2. A randomised trial of women with a previous FDCS being treated with and without a cerclage if their cervix is short (≤ 25 mm)
3. Imaging sub-study using transvaginal ultrasound and magnetic resonance imaging (MRI) to characterise any scars found to try to work out the mechanism of the problem.

PROFESSIONAL SUMMARY

Study Protocol: **Cerclage After Full-dilatation caesarean-section**

IRAS ID:261294

REC: REC 19/LO/1270

Version 2.0

Date: 10.09.19

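### Section 9.5.3 exempts expected serious cerclage-related events from expedited SAE reporting and leaves others ambiguous, and the RCT plans no by-arm maternal safety comparison

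*Combined protocol and SAP*

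**What the plan says.** Section 9.5.3, whose heading concerns adverse events that need no reporting, starts from expectedness: "Expected serious adverse events (SAEs) are those events which are expected in the patient population or as a result of the routine care/treatment". It describes cerclage as an established procedure with minimal risks, which "include infection, miscarriage, bleeding, difficulty with suture removal and preterm prelabour rupture of membranes". The next statement is: "Serious adverse events and serious adverse reactions (SARs) which are unrelated to these clinical procedures will be reported as SAEs". No matching sentence covers related events.

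A second exemption follows: "Events that are primary or secondary outcome measures are not considered to be SAEs and will be reported in the normal way", on the electronic case report form. The maternal list beneath it is premature labour, premature rupture of membranes and chorioamnionitis. A third paragraph removes common pregnancy complications, including admission for symptoms of preterm labour such as ruptured membranes or vaginal bleeding.

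The surrounding sections are as follows.
- **9.5.1:** the DMC reviews progress and outcomes as well as SAE reports.
- **9.5.2:** all AEs and SAEs are recorded from randomisation. An adverse event is defined as "Any untoward medical occurrence in a subject to whom a medicinal product has been administered", and an adverse reaction as a response related to such a product.
- **9.5.4:** all SAEs are reported within 24 hours, except those the protocol exempts.
- **4.2 (RCT endpoints):** delivery before 34 weeks; then an adverse perinatal composite, gestation at delivery, need for rescue cerclage, time from intervention to delivery, and health costs.
- **Section 8:** the RCT's secondary analyses are the endpoints of 4.2.

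**The concern.** The usual rule is that serious events related to the intervention under test are the ones most in need of prompt reporting. Here the only explicit commitment in 9.5.3 is to the unrelated ones, and the known harms of cerclage are named among events that need no report.

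The stated justification is that the procedure would be offered routinely, yet the lay summary says that cerclage for a short cervix "in women with a previous FDCS is not part of routine care".

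What is at stake is whether sites send serious procedural harms to the sponsor in time, and whether the trial report can set maternal harm beside any benefit. Cerclage is placed electively in one arm only, so under-reporting of its complications would fall mainly on that arm.

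**Working it through.** The documents give no harm rate, so the check is mainly a comparison of passages.

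**1. Does 9.5.4 restore what 9.5.3 leaves out?** Only in part. Its 24-hour duty excepts events the protocol has exempted. The five named cerclage risks are therefore not brought back. A serious procedural event that 9.5.3 does not name is not expressly exempt, so 9.5.4 can be read to cover it, while 9.5.3 commits only unrelated events. Two sites could reasonably act differently.

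**2. Is the sentence consistent with 9.5.2?** No. A reaction is related by definition there, so an unrelated serious adverse reaction cannot exist. The SAR half of the rule is empty.

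**3. Do the events under the outcome-measure exemption match the RCT's outcomes?** Membrane rupture and chorioamnionitis do not: neither is listed in 4.2.

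**4. Which cerclage risks does an RCT endpoint capture?**

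| Risk named in 9.5.3 | Other exemption in 9.5.3 | RCT endpoint in 4.2 |
|---|---|---|
| Infection (maternal) | Chorioamnionitis, as an outcome measure | None; sepsis in the composite is a perinatal outcome |
| Miscarriage | None | Counted in delivery before 34 weeks and gestation at delivery |
| Bleeding | Admission for vaginal bleeding as a symptom of preterm labour | None |
| Difficult suture removal | None | None |
| Membrane rupture | As an outcome measure, and as a reason for admission | None as an event; counted only through an early delivery |

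Of five risks, one is captured, one is captured in part, and three are not captured.

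**5. Is a maternal comparison planned elsewhere?** Section 4.1 (vii) lists other maternal and fetal morbidities from a core outcome set, but for CRAFT-OBS. Section 8 ties the RCT analyses to 4.2 and mentions no safety analysis.

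**6. Scale, on an assumption.** The planned arm size comes from section 5. Its 474 per arm for 10% versus 5% at 80% power reproduces with a continuity-corrected two-proportion formula at two-sided 5% (the significance level is not stated). Allowing for 5% loss gives 474 / 0.95 = 498.9, so 499, consistent with 500.

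Suppose serious cerclage-related maternal harm occurs at a rate p between 0.2% and 3%.
- Expected events in the cerclage arm are 500 × p: 500 × 0.002 = 1, up to 500 × 0.03 = 15.
- The chance of at least one is 1 − (1 − p)^500: 63% at p = 0.2%, 92% at 0.5%, 99% at 1%.

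The reporting rule would thus probably be called on. How many of these events would go unreported depends on how many are of the named kinds and on how sites read step 1.

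**The case against.** The case for leaving the text alone has several parts, and most narrow the point.

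- **The sentence does not say that only unrelated events are reported.** The operative duty is in 9.5.4, and 9.5.2 also counts important medical events as serious. This stands for unnamed procedural events. A reader might infer that every serious harm of cerclage escapes SAE reporting, but the documents support exemption only for the expected, named events and ambiguity for the rest. The wording may also be a drafting slip.
- **Recording is required.** Section 9.5.2 asks for all AEs and SAEs from randomisation, with open questioning at each visit and recording in case of doubt. This stands, so the data should exist.
- **The DMC sees more than SAE reports.** A reader might infer that the committee would be blind to procedural harm. Section 9.5.1 also gives it outcomes, and 9.8 leaves the content of its reviews to a charter still to be agreed. The inference is not supported. What is missing is any stated requirement that it receive exempt events by arm.
- **Some harms are caught.** Late miscarriage, and membrane rupture ending in early delivery, count in the primary endpoint. RCT women come from CRAFT-OBS, which lists maternal morbidities. This stands, but it supplies no planned comparison between randomised arms.
- **Cerclage is familiar.** The lay summary also calls it first-line prophylaxis for a short cervix in many UK units, and 1.1 calls it established. That explains why its risks are thought known. It does not show how often they occur in women with suspected cervical injury, whose care the protocol says does not routinely include it.
- **The drug-based definitions are regulatory text,** and the seriousness criteria do not depend on a drug. This stands; the mismatch is a matter of wording.

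**Conclusion.** The point holds in a limited form. Section 9.5.3 exempts the expected serious harms of the randomised procedure from expedited SAE reporting, conflicts with 9.5.2 on what a reaction is, and leaves other serious procedural events unresolved against 9.5.4. Separately, three of the five named cerclage risks have no RCT endpoint, a fourth is counted only through early delivery, and no maternal safety comparison by arm is described. The defect lies in reporting and planned comparison; data capture is provided for.

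This rests on the protocol text alone. It assumes that late miscarriage counts as delivery before 34 weeks, which fits the RCT objective in 2.2.2. The figure of 1 to 15 serious events in the cerclage arm rests on an assumed rate of 0.2% to 3% and is given for scale only.

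**What to change.** 1. Reword 9.5.3 and reconcile it with 9.5.4, so that serious events related to cerclage insertion or removal are reported as SAEs.
2. For any event kept exempt from expedited reporting, state that it is tabulated by arm for the DMC, and carry this into the DMC charter. Correct the outcome-measure list so that it matches 4.2.
3. Add to 4.2 and section 8 a by-arm summary of maternal safety events: membrane rupture, chorioamnionitis or maternal infection, bleeding, and procedure complications. Section 9.5.2 already requires these to be recorded. The summary can be descriptive, since the trial is sized for its primary endpoint.
4. As a secondary tidy-up, replace the references to a medicinal product and study drug in 9.5.2 with procedure-based wording.

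The cost is a protocol amendment to wording, a few more SAE forms and one more table. No change to the sample size or visit schedule is needed.

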9.5.4 Reporting Responsibilities

All SAEs (excepting those specified in this protocol as not requiring reporting) will be reported immediately (and certainly no later than 24hrs) by the Investigator to the GSTT R&D Office and CI for review in accordance with the current Pharmacovigilance Policy. The Chief Investigator will report to the relevant ethics committee. Reporting timelines are as follows:

The Chief Investigator (on behalf of the co-sponsors), will submit a Development Safety Update Report (DSUR) to the MHRA and REC annually.

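### Section 9.5.3 exempts delivery complications from SAE status with no severity limit, so a fatal, life-threatening or disabling one is serious under 9.5.2 yet need not be reported under 9.5.3 and 9.5.4

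*Combined protocol and SAP*

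**What the plan says.** Four parts of protocol section 9.5 bear on this.

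- **9.5.2** defines an SAE. The criteria include "Results in death", "Is life-threatening" and persistent or significant disability. A further criterion covers admission: "Required hospitalisation or prolongation of existing hospitalisation, excluding admission for birth or unrelated pregnancy condition". The Important Medical Events clause adds that an event short of these criteria also counts as serious if it puts the patient at risk or calls for intervention to avert such an outcome.
- **9.5.3** lists events that need no SAE report. One sentence begins "In addition the following common pregnancy complication events will not be considered SAEs" and ends with "delivery complications such as caesarean section or postpartum haemorrhage". Earlier, the same section says that SAEs and SARs unrelated to the clinical procedures are to be reported as SAEs.
- **9.5.4** sets the reporting duty: "All SAEs (excepting those specified in this protocol as not requiring reporting) will be reported immediately", and within 24 hours at the latest. Reports go to the R&D office and the Chief Investigator, who reports to the ethics committee.
- **9.5.1** has the DMC review study progress and outcomes, together with SAE reports.

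**The concern.** An exemption for expected pregnancy events is sensible in an obstetric trial. It keeps routine caesareans and ordinary blood loss out of the expedited stream. Such an exemption normally lifts only the admission criterion, or stops where an event becomes fatal, life-threatening or disabling. This one does neither for delivery complications: it takes them out by type, whatever their outcome.

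Every participant has had a caesarean in labour, and CRAFT-RCT allocates women 1:1 to an operation on the cervix or to standard management. Under 9.7 the TSC decides whether to stop on safety or efficacy grounds, acting on DMC recommendations. If the gravest maternal events at delivery can be left out of SAE reports, or are reported by some sites and not by others, the safety comparison between arms rests on how each site reads the text.

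**Working it through.** No arithmetic applies. The check follows one test case through the rules: a randomised woman with a life-threatening postpartum haemorrhage.

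1. **Is it an SAE under 9.5.2?** Yes, by the life-threatening criterion. The only pregnancy or birth exception in that definition sits inside the hospitalisation criterion. The death, life-threatening and disability criteria have none.

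2. **Is it an SAE under 9.5.3?** Taken literally, no. Postpartum haemorrhage is named, the lead-in says that listed events are not SAEs, and no grade or outcome is attached.

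3. **Must it be reported under 9.5.4?** Taken literally, no. The 24-hour duty excludes events that the protocol specifies as not requiring a report.

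4. **Could the item be read as lifting only the admission criterion?** Not easily. The list has six items. Five are worded as hospitalisations: for pre-eclampsia or pregnancy-induced hypertension, for symptoms of preterm labour, for discomfort, for rest, and for observation under 12 hours. Delivery complications is the sixth and the only one excluded as an event. Elsewhere the drafters did write qualifiers, as in "Perinatal death (unless unexpected at this gestation") and the item on complications of prematurity. None is attached here. Section 9.5.2 also keeps complications that arise during planned or elective admissions within AE/SAE reporting, whereas 9.5.3 takes delivery complications out.

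5. **Does other text restore the report?**
   - The sentence on unrelated SAEs applies to events that count as SAEs. The later list says these do not. The two conflict, and neither is given precedence.
   - The Important Medical Events clause and the criterion of medical significance in the principal investigator's judgement also favour reporting. Neither is stated to override 9.5.3.
   - The AE rule in 9.5.2 requires events to be recorded until 28 days after delivery, and doubtful ones too. That preserves the data but is not the 24-hour report.
   - The CRAFT-RCT endpoints in 4.2 include no maternal death, haemorrhage or other maternal morbidity. CRAFT-OBS (4.1) lists other maternal and fetal morbidities, but that is outcome collection, not SAE reporting.

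6. **Pre-eclampsia.** Only the hospitalisation is exempt, and 9.5.2 already excludes admission for an unrelated pregnancy condition. The remaining SAE criteria are not expressly switched off. This item conflicts with 9.5.2 only if it is read to cover an admission that is also fatal, life-threatening or disabling.

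**The case against.** The best defence is that a sensible site would never read the list this way. The lead-in is confined to common events, and the two examples are routine ones. Maternal death is not listed, whereas perinatal death is named where the protocol means to exempt it. The sentence on unrelated SAEs and the Important Medical Events clause both favour reporting.

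Much of this stands, and it rules out several stronger claims that a reader might infer:

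- *That a maternal death goes unreported.* The text does not say so. It only fails to require the report once the event is classed as a delivery complication, and a careful site may well report it.
- *That scar rupture or hysterectomy at delivery is exempt.* Neither is named. The wording of the item is open-ended, but the lead-in limits it to common events.
- *That pre-eclampsia is exempt whatever its severity.* Only the admission is.
- *That the infant items show a severity override was left out for mothers.* Only two of the five infant items are qualified, and the test there is expectedness, not severity.
- *That the DMC would not learn of these events.* AEs are recorded, the DMC also reviews outcomes, and the content of its reviews is left to a charter.

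What the defence does not answer is that postpartum haemorrhage is named without a grade. The word common describes the type of event and sets no limit on outcome, so a site would have to supply a limit that the protocol does not state.

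**Conclusion.** The point holds as an internal conflict between 9.5.2 on one side and 9.5.3 with 9.5.4 on the other, confined mainly to delivery complications. The gap lies in SAE classification, in the 24-hour report with the onward report to the ethics committee, and possibly in the SAE reports that reach the DMC. It does not lie in AE recording.

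The conclusion rests on the literal wording and on no assumed rate. A reader might want to turn it into a number of missed events among the 1000 planned CRAFT-RCT women. The documents give no frequency for fatal, life-threatening or disabling delivery complications and no indication of how sites would classify them, so no such number is supported. No endpoint, estimate or power figure is affected. The conflict should be resolved because it concerns the most serious maternal outcomes and is cheap to remove.

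**What to change.** Reconcile 9.5.2 to 9.5.4 by adding one sentence to 9.5.3, for example: The exemptions for common pregnancy complications do not apply to any event that meets the death, life-threatening or disability criterion of 9.5.2; such events are reported under 9.5.4 in both arms.

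This introduces no new criterion and changes no clinical care. It also settles the pre-eclampsia item. Routine caesarean section, postpartum haemorrhage that meets none of these criteria, and ordinary pre-eclampsia admissions stay exempt. The cost is a protocol amendment of one sentence and a few extra SAE forms.
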